1 INTRODUCTION

1.1 General

The purpose of this statistical analysis plan (SAP) is to provide a protocol specific description of the statistical analysis that will be performed to produce an integrated clinical/statistical report.

This SAP is based upon the following study documents:

- Protocol version: Version 1.1, 08-Nov-2019.
- eCRF last release version updated: 09-Feb-2021.

1.2 Type of Study

This is a multicenter, open-label, single-arm, phase II clinical trial to evaluate the efficacy and safety of the INCMGA00012 in progressive advanced PSqCC patients, previously treated or not with chemotherapy.

1.3 Study Population

Male patients age \geq 18 years with progressive locally advanced –not amenable to curative treatment– or metastatic PSqCC (i.e., T4 or N3 or M1) previously treated with chemotherapy regimens or patients naïve of systemic treatment.

1.4 Study Design

A total of 18 patients with unresectable locally advanced or metastatic PSqCC will be enrolled into this trial.

INCMGA00012 should be administered intravenously, at flat dose of 500 mg over one hour (\pm 15 minutes) or 30 minutes (-5/+ 15 min) using a filter on day 1 of each 28-day cycle (every 4 weeks). Infusion rate may be reduced if an infusion reaction occurs.

In the absence of progression of disease or unacceptable toxicity, treatment with INCMGA00012 will continue based on physician criteria for up to 2 years.

Tumor assessments per RECIST v.1.1 and irRECIST will be performed approximately every 8 weeks (\pm 7 days) for the first 6 months and every 12 weeks (\pm 7 days) thereafter until PD, treatment discontinuation, the start of new anti-cancer treatment, withdrawal of consent, death, or the end of study (EoS), whichever occurs first. Tumor assessments will be performed on the specified schedule regardless of treatment delays.

The primary endpoint is ORR.

For estimation of ORR, CBR, DoR, PFS, and OS, tumor response will be based on RECIST v.1.1. In patients who continue treatment beyond radiographic PD per RECIST v.1.1, tumor response (ORR, CBR, and PFS) may continue to be assessed using irRECIST criteria until study treatment discontinuation.

Safety assessments will include the incidence, nature, and severity of AEs and laboratory abnormalities graded per the NCI-CTCAE v.5.0. Laboratory safety assessments will include the regular monitoring of hematology, blood chemistry, coagulation, and thyroid function testing.

1.5 Study Schedule

Assessment Window (Days)	Screening	All cycles	End Of Treatment visit	Progression of disease	End of Study
	D -28 to -1	1(± 3 days)	28 days (± 3 days) after last dose		12 months after last study dose
Informed consent form ¹	X				
Review of eligibility criteria	X				
Demographic data and medical history ²	X				
Physical examination	X	X	X		X
ECOG performance status	X	X	X		X
Weight, Height, and Vital signs ³	X	X	X		X
Concomitant medications reporting ⁴	X	X	X		
AE reporting ⁵	X	X	X		
12-lead electrocardiogram	X		Performed as clinically indicated		
Assessment of symptoms	X	X	X		X
Tumor assessment ⁶	X		See footnote (7)		X
Hematology/Chemistry ⁸	X	X ⁽⁹⁾	X		X
TSH, free T3, free T4	X	X ⁽⁹⁾			
Coagulation panel (aPTT, INR or PTT)	X				
• Viral serology ¹⁰ and Mantoux tuberculin skin test (TST) ¹¹	X				
Urinalysis ¹²	X	Every two cycles ¹²			
Tumor samples for exploratory research ¹³	X			X	
Blood samples for exploratory research ¹⁴	X	At C3D1	X		
INCIGA00012 infusion		X		X	
Survival and anti-cancer therapy follow-up					X

Abbreviations: AE: Adverse event; ALP: Alkaline phosphatase; ALT: Alanine aminotransferase; ANC: Absolute neutrophil count; aPTT: activated partial thromboplastin time; AST: Aspartate aminotransferase; CT: Computed tomography; DNA: Deoxyribonucleic acid; ECOG PS: Eastern Cooperative Oncology Group Performance Status; EoT: End of Treatment; GGT: Gamma-glutamyl transferase; HAV: Hepatitis A virus; HBV: Hepatitis B virus; HBcAb: Hepatitis B core antibody; HBsAg: Hepatitis B surface antigen; HCV: Hepatitis C virus; HIV: Human immunodeficiency virus; INR: International normalized ratio; MRI: Magnetic Resonance Imaging; NCI-CTCAE: National Cancer Institute–Common Terminology Criteria for Adverse Events; PTT: Partial thromboplastin time; RNA: Ribonucleic acid; TSH: Thyroid-stimulating hormone; WBC: White blood cells.

1. Informed Consent Form: Signed written Informed Consent Form obtained prior to any trial-specific procedure.

2. Demographic data and medical history: Demographic data include age and self-reported race/ethnicity. Medical history comprises clinically significant diseases, surgical interventions, history of cancer (including prior antineoplastic treatments and procedures), history of smoking, alcoholism, drug addiction, as well as any medications (e.g., prescribed drugs, over-the-counter drugs, medicinal plants, homeopathic remedies, or food supplements) used by the patient in the 28 days prior to screening visit.

3. Concomitant medication reporting: Relevant concomitant medication will be recorded at screening and on an ongoing basis.

4. AE reporting: All AEs occurring during the trial and until 90 days after treatment discontinuation visit (EoT visit) have to be recorded with grading according to the NCI-CTCAE v.5.0 criteria.

5. Weight, Height, and Vital signs: Weight, height (only at screening), respiratory rate, blood pressure measurements (systolic and diastolic), pulse rate, and body temperature (oral, axillary, or tympanic temperature).

6. Tumor assessment: All measurable and evaluable lesions should be assessed and documented at the screening visit. Evaluation consists of clinical exam with evaluation of the penis and/or inguinal region and anatomical imaging performed during the screening period should consist of: a) CT of the chest, abdomen, and pelvis or MRI of the abdomen and pelvis with a non-contrast CT scan of the chest in patients for whom CT scans with contrast are contraindicated; b) Bone scan if a subject has a known history of bone metastases or has new bone pain during screening; c) Any other imaging studies as clinically indicated by the treating physician. Tumor assessments will be performed at baseline, every 8 weeks (± 7 days) for the first 6 months following first dose of study treatment, and every 12 weeks (± 7 days) thereafter, with additional scans as clinically indicated. All known sites of disease documented at screening should be re-assessed at each subsequent tumor evaluation. The same radiographic procedures and technique must be used throughout the study for each patient (bone scan will be performed only if a subject develops new or worsening symptoms or if the site believes they have attained a complete response).

7. In subjects who discontinue study treatment without documented disease progression, every effort should be made to continue monitoring their disease status by tumor imaging following the intervals as outlined in footnote 3 until the start of new anti-cancer treatment, disease progression, death, or the end of the study, whichever occurs first.

8. Hematology/Chemistry: Blood test will be performed as per local standard of care and clinical indication before treatment administration. These values should be included: hemoglobin, hematocrit, red blood cell count, platelet count, and WBC count with differential count (ANC, lymphocytes, monocytes, eosinophils, and basophiles), coagulation, chemistry with renal function analysis (serum creatinine or measured/calculated creatinine clearance or GFR), liver function (AST, ALT, ALP, GGT, total and direct bilirubin), glucose, sodium, potassium, calcium, chloride, magnesium, uric acid, total protein, albumin, and lactate dehydrogenase.

9. Cycle 1 Day 1 panel assessments are not required if the panel was performed at screening within 72 hours prior to start of study treatment.

10. Viral serology: HAV (IgM antibody), HBsAg, total HBcAb, HCV antibody; additional tests for HBV DNA or HCV RNA will be required to confirm eligibility; HIV.

11. Mantoux tuberculin skin test (TST): in case of positivity of the test results, the pulmonologists must rule out the presence of latent TBC. All patients with latent TBC will be excluded from the study.

12. Urinalysis: Urinalysis include specific gravity, pH, glucose, protein, ketones, and blood. Every 2 cycles: Cycle 1 day 1, Cycle 3 day 1, cycle 5 day 1, cycle 7 day 1, etc., before study treatment administration.

13. Tumor samples for exploratory research: A tumor tissue sample from a metastatic site or the primary tumor must be collected at the time of study entry, with the exception of patients for whom tumor biopsies cannot be obtained (e.g., inaccessible tumor or subject safety concern) that may submit an archived primary or metastatic tumor specimen only upon agreement from the Sponsor. If feasible, patients will also be given the option of providing a tumor tissue sample from metastasis or primary tumor obtained at disease progression or study termination.

14. Blood samples for exploratory research: Blood samples are required for all patients at the time of inclusion, after two cycles of study treatment, and upon progression or study termination.

Note: Additional tests will be required for all participants who are known to be HIV-positive in order to confirm CD4-positive count and the undetectable viral load, every 8 weeks during 1st year of study treatment, every 3 months during the 2nd year and every 6 months during the follow-up period. A final sample will be collected at the EoT visit or, if no separate EoT visit is performed, at the 28-day follow-up visit.

1.6 Sample Size

A total of 18 patients will be enrolled and the defined primary endpoint is ORR.

Justification of Sample Size:

The sample size calculation is based on an exact binomial test. The clinical trial is designed to demonstrate an ORR of at least 25% and to exclude a rate of less than 5% ($p_0=0.05$, $p_1=0.25$, $\alpha =0.05$, $\beta=0.80$, A'herne's exact design). At least 3 responders (18.8%) among 16 evaluable patients will be adequate to justify the investigation of this strategy in further clinical trials. Considering a drop-out rate of 10%, a sample size of 18 patients will be needed to attain 80% power at nominal level of one-sided alpha of 0.05.

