8.2 Justification of Sample Size

This is a multicenter, open-label, single arm, phase II trial evaluating the efficacy and safety of INCMGA00012 (retifanlimab) in unresectable locally advanced or metastatic PSqCC. The defined primary endpoint is ORR.

In the single arm phase II trial VinCap (57) patients with locally advanced PSqCC were treated with vinflunine. The trial evaluated CBR and ORR after 4 cycles. The 45.5% and 27.3% of patients achieved clinical benefit and objective response, respectively. These data suggest that excluding an ORR $\leq 5\%$ while targeting the improvement of the ORR to $\geq 25\%$ would be an adequate approach to assess a new antineoplastic strategy in this patient population.

The sample size calculation is based on an exact binomial test. The clinical trial is designed to demonstrate an ORR of at least 25% and to exclude a rate of less than 5% ($p_0=0.05$, $p_1=0.25$, $\alpha =0.05$, $\beta=0.80$, A'hern's exact design). At least 3 responders (18.8%) among 16 evaluable patients will be adequate to justify the investigation of this strategy in further clinical trials. Considering a drop-out rate of 10%, a sample size of 18 patients will be needed to attain 80% power at nominal level of one-sided alpha of 0.05.

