8.3 Analysis Sets

Full analysis and safety set.

The full analysis and safety set includes patients who receive at least one dose of study medication.

Per-protocol set

All patients that accomplish selection criteria, receive at least one drug exposure, and receive the protocol required study drug exposure and processing. Criteria for determining the “per protocol” (PP) group assignment would be established by the Steering Committee before the statistical analysis begins. This analysis will only occur if this set differs by $\geq 10\%$ from the full analysis set.

Exploratory analysis set

All patients with biomarker evaluable samples with the assay and alternative platforms that accomplish selection criteria and receive at least one drug exposure.

Analysis set schedule

Primary, secondary and irRECIST endpoints will be analyzed on the full analysis set, and per-protocol populations. Full analysis set will be considered the primary population for the analysis. Biomarker and correlation between biomarkers and clinical outcomes will be analyzed on exploratory analysis set. Safety analysis will be performed on the safety set.

The estimands for the study based on ICH E9 (R1) addendum will be fully described in the statistical analysis plan.

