8.4.5 Decision Rules and Adjustment of Alpha in The Study

The study would be defined as positive at final analysis, if the ORR in the INCMGA00012 (retifanlimab) arm is statistically significantly better ($p < 0.05$) than expected under the null hypothesis ($H_0: \text{ORR} \leq 5\%$). Decisions will be based on exact binomial test.

For all secondary and exploratory tests, we will use two-sided p-values with $\alpha \leq 0.05$ level of significance. The p-values emerging from these analyses will not be interpreted in a confirmative sense; they will be considered of descriptive nature only.

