8.6 Missing Data Management

Study variables could be missing for patients who withdrawn from the trial or for specific visits. We will report reasons for withdrawal. Patient with missing in response outcomes (ORR and CBR) will be considered as no responders. Other outcomes will be managed with simple imputations methods. The effect that any missing data might have on results will be assessed via sensitivity analysis of study sets.

For PFS and DoR, patients without a date of disease progression or death will be analyzed as censored observations on the date of last tumor assessment. If no post-baseline tumor assessment is available, patients will be censored at the date of randomization + 1 day. Data for patients with an event who missed two or more scheduled assessments immediately prior to the event will be censored at the last tumor assessment prior to the missed visits.

For OS, patients who are not reported as having died will be analyzed as censored observations on the date they were last known to be alive. If no post-baseline data are available, OS will be censored at the date of randomization + 1 day.

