4 ANALYSIS SETS

The following sets will be analyzed:

- **Screening:** Patients who were present at the screening visit.
- **Safety and FAS (Full Analysis Set) Set:** patients who receive at least one dose of study medication.

Efficacy and Safety endpoints will be analyzed on the Safety/FAS set.

FAS set will be considered the primary population for the analysis.

- **Per-protocol (PP) set:** All patients that accomplish selection criteria, receive at least one drug exposure, and receive the protocol required study drug exposure and processing. Criteria for determining the “per protocol” (PP) group assignment would be established by the Steering Committee before the statistical analysis begins. This analysis will only occur if this set differs by $\geq 10\%$ from the FAS set.

The primary and secondary efficacy analyses will be performed on the FAS and PP sets.

- **Exploratory Set:** All patients with biomarker evaluable samples with the assay and alternative platforms that accomplish selection criteria and receive at least one drug exposure.

Exploratory analysis will be performed on exploratory set. A separate analysis report for such assessments will be written.

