5.4.2 Primary Efficacy Analysis

ORR will be estimated with the 95% Clopper-Pearson confidence intervals and the P-value with exact binomial test.

Primary efficacy results will be reported for the FAS and PP set. Full analysis set will be considered the primary set for the analysis.

Table 1. Primary Efficacy Estimands

Estimand	Population	Variable	Intercurrent event strategy	Summary measure
Primary	FAS set	Unconfirmed ORR	- Patient with missing Unconfirmed ORR outcome will be considered as non-responders. - Patients without any post-baseline assessment will be considered as non-responders.	The number and proportion of patients with response with the 95% Pearson-Clopper CI will be calculated.
Sensitivity 1 to Primary	PP set	Unconfirmed ORR	Same as above	Same as above

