5.4.3 Decision Rules and Adjustment of Alpha for Primary Endpoint

The study would be defined as positive at final analysis, if the ORR in the INCMGA00012 arm is statistically significantly better ($p<0.05$) than expected under the null hypothesis ($H_0: ORR \leq 5\%$). Decisions will be based on exact binomial test.

For all secondary and exploratory tests, we will use two-sided P-values with alpha=0.05 level of significance. The P-values emerging from these analyses will not be interpreted in a confirmative sense; they will be considered of descriptive nature only.

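### The threshold of 3 responders and the 80% power hold for 16 analysed patients; the primary test on 18 dosed patients needs 4 responders and has about 60–69% power at an ORR of 25%

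*SAP*

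**What the plan says.** SAP 1.6 and Protocol 8.2 describe a single-stage exact binomial design with a null ORR of 5%, a target of 25% and one-sided alpha 0.05. The threshold sentence is "At least 3 responders (18.8%) among 16 evaluable patients will be adequate to justify the investigation of this strategy in further clinical trials". Protocol 8.2 then allows for 10% drop-out and concludes that "a sample size of 18 patients will be needed to attain 80% power at nominal level of one-sided alpha of 0.05"; SAP 1.6 says the same.

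The analysis sections use a different denominator. Protocol 8.3: "The full analysis and safety set includes patients who receive at least one dose of study medication". SAP 4: "FAS set will be considered the primary population for the analysis". Neither document defines an evaluable set. Patients without a response result stay in the analysis as failures. Protocol 8.6 says "Patient with missing in response outcomes (ORR and CBR) will be considered as no responders", and for the primary estimand SAP 5.4.2 (Table 1) says "Patient with missing Unconfirmed ORR outcome will be considered as non-responders".

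A positive study is defined only through the test. Protocol 8.4.5: "The study would be defined as positive at final analysis, if the ORR in the INCMGA00012 (retifanlimab) arm is statistically significantly better" (p<0.05) than expected under a null ORR of at most 5%. SAP 5.4.3 adds "Decisions will be based on exact binomial test", and the code in SAP Appendix 1 runs that test on the FAS. No responder count or power is given for 17 or 18 patients.

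**The concern.** Inflating 16 to 18 protects the design only if drop-outs leave the denominator. Under the rules above they leave it only if they are never dosed. Protocol 3.2.4 equates enrolment with treatment start, so the natural planning value for the FAS is 18, not 16.

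The exact test is discrete, and 16 is the largest sample at which 3 responders are significant. Adding one or two patients to the denominator therefore raises the threshold to 4, and power falls.

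Two things are at stake. The stated power may not belong to the primary analysis. And a result of 3 responders among 18 would meet the count in the sample-size section while failing the decision rule. In an open-label trial with investigator-assessed response, which statement governs should not be left open until the data are known.

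**Working it through.** **Inputs.** p0 = 0.05, p1 = 0.25, one-sided alpha 0.05, 16 evaluable, 10% drop-out, 18 enrolled (SAP 1.6, Protocol 8.2). The printed beta of 0.80 is the power. Primary set: all dosed, missing counted as non-response (Protocol 8.3 and 8.6; SAP 4 and 5.4.2). Success: exact binomial p<0.05 (Protocol 8.4.5, SAP 5.4.3). Those two sections do not state sidedness; one-sided is taken from the sample-size text.

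**Formula.** P(X ≥ r | n, p) = 1 − Σ_{k<r} C(n,k) p^k (1−p)^(n−k).

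**The plan's own figure.** For n = 16 and r = 3 under p = 0.05: 1 − (0.4401 + 0.3706 + 0.1463) = 0.0429. Under p = 0.25 the tail is 0.8029. Sixteen is the smallest n meeting both limits, and 16/0.9 = 17.8, rounded up to 18. The design reproduces.

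**Three responders in the primary set.**
- n = 17: 1 − (0.4181 + 0.3741 + 0.1575) = 0.0503, not below 0.05.
- n = 18: 1 − (0.3972 + 0.3763 + 0.1683) = 0.0581, not below 0.05.

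**Threshold, alpha and power by number dosed, all assessable:**

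| Dosed | Responders needed | Exact alpha | Power at 25% |
|---|---|---|---|
| 15 | 3 | 0.0362 | 0.764 |
| 16 | 3 | 0.0429 | 0.803 |
| 17 | 4 | 0.0088 | 0.647 |
| 18 | 4 | 0.0109 | 0.694 |

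**Eighteen dosed, some without a response result, at least 4 needed:**
- Each patient has a 10% chance of being unassessed: the response rate becomes 0.9 × 0.25 = 0.225, and P(X ≥ 4 | 18, 0.225) = 0.602.
- Exactly 2 of 18 unassessed: P(X ≥ 4 | 16, 0.25) = 0.595.

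**Chance of the ambiguous result.** At a true ORR of 25%, P(exactly 3 of 18) = 0.8647 − 0.6943 = 0.170.

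**Sidedness.** Doubling the p-value gives 2 × 0.01087 = 0.0217 for 4 of 18, so the threshold stays at 4. It gives 2 × 0.0429 = 0.086 for 3 of 16, which would then fail too. One-sided is the reading more favourable to the plan.

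**The case against.** The threshold sentence names its denominator and rate. Three of 18 is 16.7% and three of 17 is 17.6%, both below the printed 18.8%, so carrying that rate to 18 patients also leads to 4. On this view nothing stated is false; a statement for 17 or 18 is simply missing. That is fair for the threshold sentence alone. It does not cover the next sentence, which attributes 80% power to 18 patients, and it gives no guidance on which statement governs if 3 of 18 respond.

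If the drop-outs leave before dosing, the FAS is 16 and the design holds exactly. This stands as a condition. The documents do not say it will happen, Protocol 3.2.4 points the other way, and losing one patient instead of two (n = 17) still requires 4.

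The 60% figure needs drop-outs who are dosed, never have a recorded response, and would otherwise have responded at 25%. A patient who leaves after a documented response still counts as a responder under SAP 5.4.1.1. If the 25% target already includes early deaths and progressions, the dilution counts them twice. So 60% is a conditional lower figure; the firm ones are 69% at n = 18 and 65% at n = 17.

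The per-protocol set might number about 16, but SAP 5.4.2 makes it a sensitivity analysis, and it is run only if it differs from the FAS by at least 10%.

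Finally, the test and population are prespecified, type I error is conservative, and SAP 5.4 calls all efficacy analysis exploratory. All true. These limit the harm to overstated power and an ambiguous threshold; they do not remove it.

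**Conclusion.** The point holds. It is a mismatch between the design and analysis denominators, not an error in the n = 16 calculation. With 17 or 18 patients dosed, the primary test needs 4 responders. The chance of missing a true ORR of 25% is 31% at n = 18 if every patient is assessable (35% at n = 17), and about 40% if the planned 10% drop-outs are dosed and counted as non-responders. The plan implies 20%. Exact type I error at n = 18 is 1.1%.

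This assumes a one-sided test at 0.05 and a FAS of 17 or 18. The stated threshold and power both apply to the primary analysis only if exactly 16 patients are dosed and all have an assessable response. The threshold of 3 alone applies for any FAS from 8 to 16, with power below 80% under 16.

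**What to change.** In Protocol 8.2 and 8.4.5 and SAP 1.6 and 5.4.3, before the analysis:

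- State that the primary test is the one-sided exact binomial test on the FAS at 0.05, with success at 4 or more of 18. Add that 4 are also needed at 17, and 3 if 16 or slightly fewer are dosed.
- Give the exact alpha (1.1% at n = 18) and the power at an ORR of 25%: 69% if all 18 are assessable, and about 60% if 10% are dosed and counted as non-responders.
- Remove the sentence on 3 of 16, or label it as the n = 16 design calculation so that it is not read as the success threshold.

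This costs wording in two sections of each document and no patients; the price is a less favourable stated power. It does not restore 80%. With a threshold of 4, that is first reached at 21 patients, all assessable (power 80.8%, alpha 0.0189), if the sponsor wishes to keep the claim.
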